#### HIGHLY EFFECTIVE METHODS OF CONTRACEPTION

At a minimum, participants must agree to the use of one highly effective method of contraception as listed below:

Highly effective methods of contraception have a failure rate of < 1% when used consistently and correctly. WOCBP participants and female partners of male participants who are WOCBP are expected to use one of the highly effective methods of contraception listed below. Male participants must inform their female partners who are WOCBP of the contraceptive requirements of the protocol and are expected to adhere to using contraception with their partner. Contraception methods are as follows:

- Progestogen-only hormonal contraception associated with inhibition of ovulation.
- Hormonal methods of contraception, including oral contraceptive pills containing combined estrogen + progesterone, vaginal ring, injectables, implants, and intrauterine devices (IUDs) such as Mirena®
- Nonhormonal IUDs, such as ParaGard®
- Bilateral tubal occlusion

- Vasectomized partner with documented azoospermia 90 days after procedure
  - Vasectomized partner is a highly effective birth control method provided that partner is the sole sexual partner of the WOCBP trial participant and that the vasectomized partner has received medical assessment of the surgical success.
- Intrauterine hormone-releasing system (IUS)
- Complete abstinence
  - Complete abstinence is defined as the complete avoidance of heterosexual intercourse
  - Complete abstinence is an acceptable form of contraception for all study drugs and must be used throughout the duration of the study treatment (plus 5 half-lives of the investigational drug plus 30 days);
  - It is not necessary to use any other method of contraception when complete abstinence is elected;
  - Participants who choose complete abstinence must continue to have pregnancy tests, as specified in Section 7.
  - Acceptable alternate methods of highly effective contraception must be discussed in the event that the participant chooses to forego complete abstinence.
  - The reliability of sexual abstinence needs to be evaluated in relation to the duration of the clinical trial and the preferred and usual lifestyle of the participant.

#### UNACCEPTABLE METHODS OF CONTRACEPTION

- 1) Periodic abstinence (calendar, symptothermal, post-ovulation methods)
- 2) Withdrawal (coitus interruptus)
- 3) Spermicide only
- 4) Lactation amenorrhea method (LAM)

#### 4.4.2 Exclusion Criteria

##### 1. *Target Disease Exceptions*

- a) Participants with previous brain metastases are eligible provided that they are treated and asymptomatic not requiring steroids or anticonvulsants, and have stable disease at the screening tumor assessment. A 4 week disease stable interval as confirmed by MRI or CT brain w/ contrast (Table 7.4-2) is required after treatment of brain metastases before initiation of thoracic radiation therapy. In addition, subjects must have been either off corticosteroids, or on a stable or decreasing dose of  10 mg daily prednisone (or equivalent).

b) Participants who have received prior chest radiation which at the discretion of the treating radiation oncologist precludes delivery of protocol radiation therapy as outlined in section 5 .

c) Carcinomatous meningitis

d) Pleural effusion that cannot be controlled with appropriate interventions

e) All toxicities attributed to prior anti-cancer therapy must have been resolved to Grade 1 (NCI CTCAE Version 4) or baseline before administration of study drug(s) other than:

i) Patients with toxicities attributed to prior anti-cancer therapy that either are not expected to resolve and/or result in long-lasting sequelae, such as neuropathy after platinum-based therapy, or are not expected to interfere with treatment on study, such as fatigue, alopecia, or grade 2 hematologic toxicity are eligible.

## 2. *Medical History and Concurrent Diseases*

a) Women who are pregnant or breastfeeding

b) Active, known, or suspected autoimmune disease. Patients with an autoimmune paraneoplastic syndrome requiring concurrent immunosuppressive treatment are excluded. Patients with type I diabetes mellitus, hypothyroidism only requiring hormone replacement, skin disorders (such as vitiligo, psoriasis, or alopecia) not requiring systemic treatment, or conditions not expected to recur in the absence of an external trigger are permitted to enroll

c) A condition requiring systemic treatment with either corticosteroids (> 10 mg daily prednisone equivalent) or other immunosuppressive medications within 14 days of study initiation. Corticosteroids with minimal systemic absorption (inhaled or topical steroids) and adrenal replacement steroid doses > 10 mg daily prednisone equivalent are permitted in the absence of active autoimmune disease

d) Prior therapy with anti-PD-1, anti-PD-L1, anti-PD-L2, anti-CD137, or anti-CTLA-4 antibody (including ipilimumab or any other antibody or drug specifically targeting T cell co-stimulation or checkpoint pathways)

e) Interstitial lung disease that is symptomatic or may interfere with the detection or management of suspected drug-related pulmonary toxicity

f) Any patient requiring supplemental oxygen therapy

g) Previous malignancies (except non-melanoma skin cancers, and the following in situ cancers: bladder, gastric, colon, endometrial, cervical/dysplasia, melanoma, or breast) unless a complete remission was achieved at least 2 years prior to study entry AND no additional therapy is required during the study period

h) Known medical condition that, in the investigator's opinion, would increase the risk associated with study participation or study drug(s) administration or interfere with the interpretation of safety results

i) Major surgery or significant traumatic injury that is not recovered at least 14 days before the initiation of thoracic radiation therapy.

### *3. Physical and Laboratory Test Findings*

a) Positive test for hepatitis B virus (HBV) using HBV surface antigen (HBVsAg) test or positive test for hepatitis C virus (HCV) using HCV ribonucleic acid (RNA) or HCV antibody test indicating acute or chronic infection

i) Individuals with a positive test for HCV antibody but no detection of HCV RNA indicating no current infection are eligible

b) Known medical history of testing positive for human immunodeficiency virus (HIV) or known medical history of acquired immunodeficiency syndrome (AIDS)

c) Inadequate hematologic function defined by:

i) Absolute neutrophil count (ANC)  $< 1,000/\text{mm}^3$ .

ii) Platelet count  $< 100,000/\text{mm}^3$ , or

iii) Hemoglobin level  $< 8.0 \text{ g/dL}$

d) Inadequate hepatic function as defined by either:

i) Total bilirubin level  $\geq 1.5$  times the ULN (except patients with Gilbert Syndrome, who are excluded if total bilirubin  $\geq 3$  times ULN), or

ii) AST and ALT levels  $\geq 2.5$  times the ULN or  $\geq 5$  times the ULN if liver metastases are present

e) Inadequate pancreatic function as defined by either:

i) Lipase  $> 1.5$  ULN. Participants with lipase  $> 1.5$  ULN may enroll if there are neither clinical nor radiographic signs of a pancreatitis

ii) Amylase  $> 1.5$  ULN. Participants with amylase  $> 1.5$  ULN may enroll if there are neither clinical nor radiographic signs of a pancreatitis

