#### **6.5.3.4 Discontinuation Criteria**

Treatment with study therapy should be permanently discontinued for the following:

- Any Grade 2 drug-related uveitis or eye pain or blurred vision that does not respond to topical therapy and does not improve to Grade 1 severity within the re-treatment period OR requires systemic treatment
- Any Grade 3 non-skin, drug-related AE lasting > 7 days, with the following exceptions:
  - Grade 3 drug-related uveitis, pneumonitis, bronchospasm, neurologic toxicity, hypersensitivity reaction, or infusion reaction of any duration requires discontinuation
  - Grade 3 drug-related laboratory abnormalities do not require treatment discontinuation except:
    - ◆ Grade 3 drug-related thrombocytopenia > 7 days or associated with bleeding requires discontinuation
    - ◆ Any drug-related liver function test (LFT) abnormality that meets the following criteria require discontinuation:
      - AST or ALT > 8 x ULN
      - Total bilirubin > 5 x ULN
      - Concurrent AST or ALT > 3 x ULN and total bilirubin > 2 x ULN
- Any Grade 4 drug-related AE or laboratory abnormality, except for the following events which do not require discontinuation:
  - Grade 4 neutropenia  $\leq$  7 days
  - Grade 4 lymphopenia or leukopenia
  - Isolated Grade 4 electrolyte imbalances/abnormalities that are not associated with clinical sequelae and are corrected with supplementation/appropriate management within 72 hours of their onset
  - Grade 4 amylase or lipase abnormalities that are not associated with symptoms or clinical manifestations, or radiographic signs of pancreatitis. It is recommended to consult with the Principal Investigator for Grade 4 amylase or lipase abnormalities
  - For Grade 4 endocrinopathy AEs such as adrenal insufficiency, ACTH deficiency, hyper or hypothyroidosis, or glucose intolerance, which resolve or are adequately controlled with physiologic hormone replacement (steroids, thyroid hormones) or glucose controlling agents, respectively, retreatment can be considered after discussion with the Principal Investigator
- Any dosing interruption lasting > 6 weeks from the last dose with the following exceptions:

- Dosing interruptions to allow for prolonged steroid tapers to manage drug-related AEs are allowed. Prior to re-initiating treatment in a participant with a dosing interruption lasting > 6 weeks from the last dose, the Principal Investigator must be consulted

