## **8.6 Potential Drug-Induced Liver Injury (DILI)**

Wherever possible, timely confirmation of initial liver-related laboratory abnormalities should occur prior to the reporting of a potential DILI event. All occurrences of potential DILIs, meeting the defined criteria, must be reported as SAEs (see Section 8.1.1 for reporting details).

Potential drug induced liver injury is defined as:

1. AT (ALT or AST) elevation > 3 times upper limit of normal (ULN)

AND

2. Total bilirubin > 2 times ULN, without initial findings of cholestasis (elevated serum alkaline phosphatase),

AND

3. No other immediately apparent possible causes of AT elevation and hyperbilirubinemia, including, but not limited to, viral hepatitis, pre-existing chronic or acute liver disease, or the administration of other drug(s) known to be hepatotoxic.

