## 9.4 Endpoints

### 9.4.1 Primary Endpoints

**Part I: Safety Run In Phase I:** Unacceptable toxicity status at the end of 13-week safety observation period with unacceptable toxicity defined as:

- Any grade 4 immune related adverse event (irAE),
- Any  $\geq$  grade 3 noninfectious pneumonitis,
- 
- Any grade 3 irAE, excluding pneumonitis, that does not downgrade to grade 2 within 7 days after onset of the event despite optimal medical management including systemic corticosteroids or does not downgrade to  $\leq$  grade 1 or baseline within 14 days,
- Liver transaminase elevation  $> 8 \times$  ULN or total bilirubin  $> 5 \times$  ULN,
- Any  $\geq$  grade 3 non-irAE, except for the following exclusions:
  - grade 3 fatigue lasting  $\leq$  7 days
  - grade 3 endocrine disorder (thyroid, pituitary, and/or adrenal insufficiency) that is managed with or without systemic corticosteroid therapy and/or hormone replacement therapy and the participant is asymptomatic
  - grade 3 infusion-related reaction (first occurrence and in the absence of steroid prophylaxis) that resolves within 6 hours with appropriate clinical management
  - grade 3 or 4 neutropenia that is not associated with fever or systemic infection that improves by at least 1 grade within 3 days.

**Part II: Phase II:** The primary endpoint is 6-month PFS status. PFS is defined as the duration from date of registration to date of first documentation of progression assessed by local investigator or symptomatic deterioration (as defined above) or death due to any cause. Patients last known to be alive without report of progression are censored at date of last disease assessment. For patients with a missing scan (or consecutive missing scans) whose subsequent scan determines progression, the expected date of the first missing scan (as defined by the disease assessment schedule) will be used as the date of progression.

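### Read literally, the transaminase exclusion in 4.4.2, 3(d)(ii) needs both AST and ALT to be raised, so it sets no limit on a single raised enzyme, unlike the protocol's other hepatic rules

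*Combined protocol and SAP*

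**What the plan says.** Section 4.4.2, item 3(d), opens with "Inadequate hepatic function as defined by either" and gives two alternatives. Limb (i) concerns total bilirubin. Limb (ii) concerns "AST and ALT levels" at or above 2.5 times ULN, or at or above 5 times ULN if there are liver metastases.

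Three later sections set transaminase limits for other purposes:

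- Section 6.5.3.4 (discontinuation): "AST or ALT > 8 x ULN", under the lead-in "Any drug-related liver function test (LFT) abnormality that meets the following criteria require discontinuation".
- Section 8.6 (potential drug-induced liver injury): "AT (ALT or AST) elevation > 3 times upper limit of normal (ULN"), together with a bilirubin condition and the absence of another apparent cause.
- Section 9.4.1 (unacceptable toxicity, Part I primary endpoint): "Liver transaminase elevation" above 8 times ULN, or total bilirubin above 5 times ULN. This bullet carries no condition on baseline value or attribution.

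Two other exclusions in 4.4.2 can bear on the same patient. Item 1(e) says "All toxicities attributed to prior anti-cancer therapy must have been resolved to Grade 1" or to baseline before study drug, with listed exceptions. Item 2(h) covers a known medical condition that, in the investigator's opinion, "would increase the risk associated with study participation or study drug(s) administration" or would interfere with interpreting the safety results.

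**The concern.** In an inclusion criterion, 'and' tightens the rule. In an exclusion criterion it loosens it, because both conditions must be met before anyone is kept out. Limb (ii) therefore catches only patients in whom both enzymes are raised, and one enzyme can be as high as it likes while the other stays below the limit.

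Section 1.4 names liver toxicity among the clinically relevant adverse events of the combination, and limb (ii) is the only numeric transaminase limit at entry. If it leaves a single enzyme unbounded, part of the liver screen depends on attribution or on the investigator's opinion. There is a secondary problem for the lead-in: the liver bullet in 9.4.1 does not say how a value that was already high at entry should be classified.

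**Working it through.** No sample-size, alpha or power figure depends on this criterion, so there is no figure in the plan to reproduce. The check applies limb (ii) to example patients under each reading.

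**Inputs.** The limit L is 2.5 times ULN without liver metastases and 5 times ULN with them (4.4.2, 3(d)(ii)). The comparison level is above 8 times ULN (6.5.3.4 and 9.4.1). The patients are hypothetical.

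**Rules.** Literal reading: exclude if AST ≥ L and ALT ≥ L. Either-enzyme reading: exclude if AST ≥ L or ALT ≥ L.

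| AST / ALT (x ULN) | Liver metastases | Literal 'and' | Either enzyme | One value > 8 |
|---|---|---|---|---|
| 3 / 1 or 1 / 3 | no | not excluded | excluded | no |
| 3 / 3 | no | excluded | excluded | no |
| 9 / 1, 1 / 9 or 9 / 2.4 | no | not excluded | excluded | yes |
| 9 / 9 | no | excluded | excluded | yes |
| 3 / 1, 1 / 3 or 3 / 3 | yes | not excluded | not excluded | no |
| 9 / 1, 1 / 9 or 9 / 2.4 | yes | not excluded | excluded | yes |
| 9 / 9 | yes | excluded | excluded | yes |

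The two readings differ exactly when one enzyme is at or above L and the other is below it.

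**Distance to 8 times ULN.** On the either-enzyme reading every admitted value is below L, so the ratio of 8 to the highest admitted value exceeds 8 / 2.5 = 3.2 without liver metastases and 8 / 5 = 1.6 with them. On the literal reading a single enzyme has no upper bound, so limb (ii) guarantees no such margin. These are ratios of stated limits and say nothing about how often such a patient presents.

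**Is the literal reading a fair one?** Elsewhere the protocol gives its connectives meaning. Section 6.5.3.4 uses 'or' between the two enzymes and, in its next-but-one line, 'and' to require a raised transaminase together with a raised bilirubin. Section 8.6 uses 'or' between the enzymes. Section 9.4.1 speaks of a transaminase elevation and asks for no pair. Within item 3 itself, the blood-count limits in 3(c) are joined by 'or', and lipase and amylase in 3(e) are listed as separate alternatives.

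**What else could exclude a 9 / 1 patient?**

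- Item 1(e) can, if the elevation is attributed to prior anti-cancer therapy and none of its exceptions applies. It does not reach an elevation caused by, for example, liver metastases, a group that limb (ii) expressly provides for.
- Item 2(h) can, if the investigator so judges. It sets no number.
- Limb (i) can, if bilirubin is also raised, and item 3(a) can, if hepatitis B or C is the cause.

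What is left is an isolated transaminase elevation, not attributed to prior therapy (or within the 1(e) exceptions), with acceptable bilirubin and hepatitis tests, that the investigator does not exclude.

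**The case against.** The strongest reply is that the phrase merely names the two tests to which the limit applies, so that either one at the limit excludes. That is a possible reading, and this may well be a drafting slip rather than a chosen rule. It does not dispose of the point: a limit that two sites can apply differently needs correcting, particularly as 4.4.2 closes by insisting that all eligibility criteria be fully met.

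The rest of the reply concerns consequences, and most of it stands. A reader might infer any of the following, none of which the documents support:

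- *Such a patient is eligible.* Passing limb (ii) is not eligibility. All entrants begin radiotherapy within 8 weeks of platinum chemotherapy, so 1(e) covers an obvious cause of a raised enzyme, and 2(h) remains.
- *The patient already meets the discontinuation rule at entry.* The 6.5.3.4 limit applies to drug-related abnormalities only, and a pre-treatment value is not one. Section 8.6 likewise needs further conditions, so it is comparable in wording, not as a threshold.
- *The patient counts towards the three events that stop the lead-in before any drug is given.* Sections 4.1 and 9.1 count patients who *develop* unacceptable toxicity, and Section 8 defines an adverse event as new or worsening. A stable pre-existing value is hard to fit to either. What does stand is that the liver bullet in 9.4.1 is silent on baseline, so classification could be disputed.
- *The liver screen is removed.* The bilirubin limb, the hepatitis tests and the exclusion of patients with both enzymes raised all remain.
- *Registration staff check the literal 'and'.* Section 6.4 mentions an eligibility checklist, but its wording is not in the documents.

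**Conclusion.** The concern holds in a limited form. Taken literally, 3(d)(ii) does not exclude a patient with one raised transaminase at any level, which is out of line with the single-enzyme wording in 6.5.3.4, 8.6 and 9.4.1. Items 1(e) and 2(h) narrow the gap but do not close it, because neither supplies a numeric transaminase limit.

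In size, it is an unbounded value for one enzyme in a subgroup whose frequency the documents do not allow one to estimate. The effect on the lead-in is a possible dispute over classification, not a demonstrated route to stopping the study. The conclusion rests on reading 'and' as the protocol uses it in its other hepatic rules; if every site reads the phrase as meaning either enzyme, only the ambiguity remains. It makes no judgement on whether the multiples of ULN are the right ones.

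**What to change.** Reconcile the connective in 4.4.2, 3(d)(ii), with 6.5.3.4, 8.6 and 9.4.1 by stating outright whether one raised enzyme is enough to exclude. The wording 'AST or ALT' would match those sections and leave the stated multiples as they are. If both enzymes are really meant to be required, the protocol should say so and give the reason. Check that the eligibility checklist in 6.4 carries the same wording. While the text is open, state in 9.4.1 how a transaminase value already raised at entry is to be classified in the lead-in.

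The cost is a one-word change in the criterion, a clarifying sentence in 9.4.1 and a check of the checklist. No test is added, since the screening panel in Table 7.1-1 already includes both enzymes. With 'or', some patients with one isolated raised enzyme may be excluded who would otherwise enter. No sample size, alpha or power figure changes.

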### *4. Allergies and Adverse Drug Reaction*

a) History of allergy or hypersensitivity to any of the study drugs or study drug components

### *5. Other Exclusion Criteria*

a) Prisoners or individuals who are involuntarily incarcerated

b) Individuals who are compulsorily detained for treatment of either a psychiatric or physical (eg, infectious disease) illness

Eligibility criteria for this study have been carefully considered to ensure the safety of the study participants and that the results of the study can be used. It is imperative that participants fully meet all eligibility criteria.

#### **4.4.3 Women of Childbearing Potential**

A woman of childbearing potential (WOCBP) is defined as any female who has experienced menarche and who has not undergone surgical sterilization (hysterectomy or bilateral oophorectomy) and is not postmenopausal. Menopause is defined as 12 months of amenorrhea in a woman over age 45 years in the absence of other biological or physiological causes. In addition, females under the age of 55 years must have a serum follicle stimulating hormone (FSH) level  $> 40$  mIU/mL to confirm menopause. Females treated with hormone replacement therapy (HRT) are likely to have artificially suppressed FSH levels and may require a washout period in order to obtain a physiologic FSH level. The duration of the washout period is a function of the type of HRT used. The duration of the washout period below are suggested guidelines and the investigators should use their judgment in checking serum FSH levels. If the serum FSH level is  $> 40$  mIU/ml at any time during the washout period, the woman can be considered postmenopausal:

- 1 week minimum for vaginal hormonal products (rings, creams, gels)
- 4 week minimum for transdermal products
- 8 week minimum for oral products

Postmenopausal women may continue HRT after FSH testing is completed and postmenopausal status is confirmed. Other parenteral products may require washout periods as long as 6 months.

### **4.5 Concomitant Treatments**

#### **4.5.1 Prohibited and/or Restricted Treatments**

The following medications are prohibited during the study:

- Immunosuppressive agents (except to treat a drug-related AE or an autoimmune paraneoplastic syndrome). Participants with an autoimmune paraneoplastic syndrome at enrollment requiring concurrent immunosuppressive treatment are not eligible;
- Systemic corticosteroids  $> 10$  mg daily prednisone equivalent, except as stated in Section 4.4.2 or to treat a drug-related AE;
- Any concurrent systemic antineoplastic therapy (ie, chemotherapy, hormonal therapy, immunotherapy, standard or investigational agents for the treatment of cancer);
- Supplemental oxygen therapy
- Surgical resection of tumor;

- Note: in addition to the study prescribed thoracic radiotherapy, the following radiotherapy is permitted:
  - Palliative bone radiotherapy as described in Section 4.5.2
  - Palliative radiotherapy to a single metastatic site, other than bone, in participants who do not require immediate initiation of second-line systemic anti-cancer therapy. See Section 4.5.2 for additional restrictions.

